## Methods and procedures

### Design

This study is a non-randomized, single arm, multi-center mixed methods clinical trial in a naturalistic setting (see Figure 1 for an overview of the study design). Participants are recruited in a real life setting in Norwegian specialised mental health care. After recruitment participants fill out questionnaires pre, interim and post treatment, in addition to follow up at 6 and 12 months after completing treatment. Interim measures are collected after six weeks. After the treatment intervention, some participants are invited to an in-depth qualitative interview.

[figure not shown]

Figure 1. Study design.

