## Power analyses

In a multilevel model, the fixed effects are comparable to ordinary repeated t-tests, and thus, using this as a proxy model with a moderate effect size ( $d = 0.6$ ), power = 0.8, alpha = 0.05, tails = "two.sided", we need 25 subjects for detecting a single main effect Murayama, Usami and Sakaki (2022); see [Summary-statistics-based power analysis \(shinyapps.io\)](#). But, as stated by Van Voorhis and Morgan (2007): "*if the circumstances allow, a researcher would have better power to detect a small effect size with approximately 30 participants per variable*" (page 48). Following this rule of thumb, we plan for 30 participants per predictor (unique main effects), thus a total sample size of 300 participants. Calculating a drop-out rate of 30% gives a total sample size of  $N = 390$ . Calculating power for indirect effects – or mediation – we used the following online shiny app [Monte Carlo Power Analysis for Indirect Effects \(shinyapps.io\)](#), published by Schoemann, Boulton and Short (2023). Using (El Alaoui et al. 2015) as a proxy study for the direction and strength of association between our variables, they found that both treatment credibility and treatment adherence were significantly predictors of faster change and lower post treatment scores in a routine psychiatric care based ICBT for social anxiety disorder. In the same study, a high level of treatment credibility was associated with higher treatment adherence. Hence, defining X = treatment credibility, M = treatment adherence and Y = treatment outcomes, we set the correlation of X-M (a-path) = 0.3 ( $SD = 1$ ), X-Y (c-path) = 0.30 ( $SD = 1$ ) and M-Y (b-path) = 0.30 ( $SD = 1$ ), power = 0.8, alpha = 0.05, setting random seed to "0512", using 5000 replications with 20000 Monte Carlo draws per replication, we need  $N = 155$  to have a power of 0.80, 95% CI [0.79-0.82].

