## Procedure

Inclusion will be open for 18 months, planned from September 2024. Participants will be recruited from outpatient specialised mental health care facilities in the Western Norway Regional Health Authority and South-Eastern Norway Regional Health Authority. After recruitment, each participant will undergo an assessment for eligibility where inclusion and exclusion criteria are evaluated. If eligible, participants are asked to sign a written informed consent to participation before enrolment in the study. Participants will receive access to the program after consent has been given, using level four secure login, for example BankID or Buypass ID. Participants receive a short tutorial of the program by their eTherapist. When logged in the first time, and as a mandatory task before given access to the program, participants are asked to revise their consent in regards to their unidentifiable data being used in research. Participants can at any time during treatment withdraw their consent. In this case they will be able to continue treatment, but their user data will not be exported for research purposes. Demographic variables and questionnaires will be given as a mandatory task before the first module and are registered directly in the program. The program is set to take 12 weeks to finish.

The main form of contact between participant and eTherapist will be via asynchronous messages. If asked for by the participant, or evaluated as necessary by the eTherapist there will be contact via phone or face-to-face. If a participant fails to log in for more than seven days the eTherapist will make contact via phone or SMS giving them an appointment to evaluate further progress. If a patient drops out of the program the eTherapists are to use their local procedures to how this person is taken care of, see also section for Ethical Considerations.

After 12 weeks the participants will be given a concluding session face-to-face where the next step is decided: End treatment, further treatment within the specialist mental health

care services or referred to a different treatment option. Regardless of this the participants will have access to the treatment program, without therapist contact, for six months after completion.

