Participants will be asked to take part in a voluntary interview with a research fellow in the project. After six and 12 months, participants will be notified via SMS asking them to fill out self-report questionnaires. They will be given two reminders via SMS if they do not respond. If they do not fill in the forms after the two reminders they will be regarded as lost to follow up.

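### The post assessment has no date and follow-up is counted from completing treatment, so the timing and collection of outcomes for people who stop the programme early are undefined

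*Protocol*

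**What the plan says.** **Schedule.** Under Design, participants "fill out questionnaires pre, interim and post treatment, in addition to follow up at 6 and 12 months after completing treatment". One occasion within treatment is given a time: "Interim measures are collected after six weeks". The post assessment is given none.

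**Programme length.** Under Procedure, "The program is set to take 12 weeks to finish", and "After 12 weeks the participants will be given a concluding session face-to-face where the next step is decided". No questionnaire is attached to that session. Baseline questionnaires are a mandatory task inside the program before the first module. No route is described for the post questionnaire.

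**Follow-up contact.** Under Procedure, "After six and 12 months, participants will be notified via SMS asking them to fill out self-report questionnaires", and "They will be given two reminders via SMS if they do not respond". People who still do not answer are counted as lost to follow-up. Prompt and reminders are described for these two occasions only.

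**People who leave.** Under Procedure, "If a patient drops out of the program the eTherapists are to use their local procedures to how this person is taken care of". The section on participant drop-out under Ethical considerations offers them other treatment. Both passages concern care, and neither mentions outcome assessment.

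**Outcome and analysis.** The degree of sick leave, a primary outcome, is self-reported (Measures), and no second source for it is named. Statistical analyses plans mixed models in which data may be missing at random. Power analyses states: "Calculating a drop-out rate of 30% gives a total sample size of" 390, without saying whether drop-out means leaving the programme or leaving data collection.

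**The concern.** Taken literally, the schedule leaves someone who stops at, say, module 3 without a post date, because post is not tied to the calendar. It also leaves that person without a start for the follow-up clock, because treatment was never completed. Sites applying the text could reasonably differ: one might send the post questionnaire at week 12 regardless, another might send nothing.

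This belongs in the protocol and cannot be left to an analysis plan, since no analysis can recover a score that was never requested. H1a, H1b and H3 are pre-to-post claims with gains held at follow-up, and H4, H6 and H7 also use return to work or absenteeism at post. The protocol's own Summary of knowledge reports that treatment credibility predicts drop-out, adherence and outcome, and that adherence predicts outcome. By its own account, then, people who leave may well fare differently from people who stay, and missing outcomes among leavers would not be a harmless random loss.

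**Working it through.** **1. The occasions side by side, for someone who stops early**

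| Occasion | Date in the text | Prompt or reminder in the text | Defined for an early leaver? |
|---|---|---|---|
| Baseline | Before module 1 | Mandatory task in the program | Yes |
| Interim | Six weeks | None stated | Date yes, route not stated |
| Post | None | None stated | No |
| 6 and 12 months | Counted from completing treatment | SMS and two reminders | Sent to participants generally, but no start date |

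The gap is at post and at the start of the follow-up clock. Someone who leaves before week 6 and is not pursued contributes a baseline only. The mixed model then has to infer that person's course from people with later data.

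**2. How many people could be affected**

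Inputs from Power analyses: 300 participants before drop-out, drop-out 30%, total 390.

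- The stated total is reproduced as 300 × 1.30 = 390. (Dividing by the retained share gives 300 / 0.70 = 429. That is a separate matter and plays no part here.)
- If the 30% means leaving the programme: 390 × 0.30 = 117 leavers and 390 − 117 = 273 who stay.
- If the 30% means leaving data collection, the number of programme leavers is not given.

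**3. What uncollected outcomes could do**

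The documents give no outcome for leavers, so this is an illustration on assumed values. Take a 30% share of leavers and a standardised pre-post change of 0.80 in those who stay.

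Average over all who start = 0.70 × (effect in stayers) + 0.30 × (effect in leavers).

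| Assumed effect in leavers | Average over all who start | Overstatement if 0.80 is reported |
|---|---|---|
| 0 | 0.56 | 0.80 / 0.56 − 1 = 43% |
| 0.2 | 0.62 | 0.80 / 0.62 − 1 = 29% |
| 0.4 | 0.68 | 0.80 / 0.68 − 1 = 18% |
| 0.8 | 0.80 | 0% |

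For H1b, on the same footing: if 50% of stayers return fully to work and 0%, 10%, 20%, 30% or 50% of leavers do, the rate over all who start is 35%, 38%, 41%, 44% or 50%.

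These figures compare a stayers-only average with the average over everyone. They show the size of the problem if leavers contribute nothing informative after baseline. Interim scores from leavers would bring the mixed-model estimate closer to the truth. If people leave because they have recovered and gone back to work, the error would run the other way.

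**The case against.** The strongest case on the other side is that this is loose wording which the rest of the text resolves.

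- **Week 12 may be the anchor.** The programme is set at 12 weeks and a concluding session follows, so completing treatment can be read as the end of a fixed 12-week period. This is plausible. But the 12 weeks is a planned duration, the session serves to decide further care, and no questionnaire is linked to it.
- **Follow-up is not limited to completers.** The SMS goes to participants at large, and loss to follow-up is defined by non-response, not by leaving the programme. This stands. A reader might infer that drop-outs are excluded from assessment, but no passage says so. What the SMS passage does not supply is a start date for those who never complete, or any cover for the post occasion.
- **Disengaging users are contacted.** More than seven days without login triggers a phone or SMS contact and an appointment. That contact is about progress in the programme, not about questionnaires.
- **The mixed model uses all available data.** True, so it would be wrong to say that the results simply describe completers. Credibility is also measured at baseline and listed as a predictor, which makes missing at random more plausible in models that include it. It does not help where leaving depends on unrecorded change after the last score.
- **Some content is not at hand.** Figure 1 and the implementation directive in Appendix C may give assessment times. If Figure 1 places post at week 12, the post date is settled. The text would still need to say that people who stop are included.

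Two further inferences are tempting and unsupported. One is that the protocol expects 30% to leave the programme, when the rate is undefined. The other is that slow users have later post dates, which nothing in the text describes.

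**Conclusion.** The point holds in a limited form. The protocol text leaves the post date undefined and starts the follow-up clock at an event that non-completers do not reach. It also describes prompts and reminders only for the 6- and 12-month occasions. It does not exclude non-completers: the interim is dated, follow-up is addressed to participants in general, and week 12 may well be what is meant.

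The consequence is conditional. If leavers' outcomes are not collected, H1a, H1b and H3 lean on those who stay and on missing at random. The size cannot be determined from the documents. It affects about 117 of 390 people only if the 30% means leaving the programme. On the assumed values above, a stayers-only result would overstate the average effect by between 0% and 43%, and the planned mixed model would soften this to the extent that leavers supply interim data. That the results favour the programme is a risk, not an established fact. The change is still worth making, because it bears on a primary outcome with no stated fallback source and costs little.

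**What to change.** In Design and Procedure:

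1. Date every assessment from the baseline questionnaire for everyone who starts: interim at week 6, post at week 12, follow-ups 6 and 12 months after the week-12 date. State that this applies regardless of modules completed and also when treatment has stopped, unless research consent has been withdrawn.
2. Use the SMS link and two reminders already planned for follow-up for the post questionnaire as well.
3. State that non-response at 6 months counts as one missed occasion and that the 12-month questionnaire is still sent. The text does not say that it would be withheld, but the lost-to-follow-up wording leaves this open.

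It would also help to say in Power analyses whether the 30% refers to leaving the programme or to missing outcome data.

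The cost is a few sentences and one more use of an existing SMS function. No sample-size figure, eligibility criterion or part of the treatment changes. The downside is that some post scores will come from people who have not finished the modules, so the average effect may look smaller. That average then describes everyone who starts the programme.

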## Sample

Inclusion criteria for the sample are 1) being an outpatient in specialised mental health care service, 2) above 18 years old, 3) full or graded sick leave, or on work assessment allowance 4) primary diagnosis of F30 – F40 (ICD-10), 5) currently employed.

Exclusion criteria are 1) ongoing psychotic disorder and/or mania, 2) ongoing substance abuse, incl. sedative medications, 3) ongoing episode of major depression, 4) organic brain disease, 5) severe reading and writing difficulties.

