### Publications and communication of the results

### References

## Background and status of knowledge

*“Twelve billion working days are lost every year to depression and anxiety alone”.*

(WHO 2024)

Mental health problems and disorders affect one in every five amongst the working-age adults in the OECD countries (Kessler et al 2005). And as many as two thirds of new disability pensions are due to poor mental health (OECD 2016). This constitutes a major public health challenge that also has large implications for work participation and productivity. People with mental health conditions are more often unemployed, more often in need of sick-leave and are absent for longer durations (OECD 2020). People with mental disorders report a 30% lower employment rate than those with no mental disorders (OECD 2021). Of employees reporting mental disorders, half had days away from work, compared to under a third of people without mental ill-health. As many as two thirds of new disability pensions are due to poor mental health (OECD 2016). Mental health issues are also the largest cause of disability pensioning for adults from 25 - 39 years (Brage & Thune, 2020). Mental disorders as a cause of sick-leave and disability pension have increased in the OECD countries and Norway. Major depression and anxiety are the most prevalent of the mental disorders and are therefore named common mental disorders (CMD). CMD have become a major cause of work absenteeism, with 30% of all sick leave in Norway being due to CMDs in 2024, which is an increase from 20% in 2019 (NAV 2024; Gundersen & Medalen, 2019).

The option for paid sick-leave is an important tool and an effective way to stop deterioration when used correctly. However, long-term sick leave can also have adverse consequences (Folkehelseinstituttet, 2015). This seems especially relevant for people with mental disorders due to the adverse effects of absenteeism on mental health and negative

effects on workplace relationships due to the stigma associated with mental disorders (OECD 2016; Gundersen & Medalen).

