### **Study aims**

The main aim of the current study is to investigate the utility and use of a digital transdiagnostic work-focused CBT treatment program for patients with common mental health disorders on sick leave or work assessment allowance. This includes the user experience of participation and experienced utility of the treatment program. Secondary aims are related to mediators and moderators of treatment efficacy and the participants' experience with the program.

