*Secondary outcome measures:* The Generalized Anxiety Disorder-7 (GAD-7; (Spitzer et al. 2006) is a measure of worry and anxiety and consists of seven items scored from 0 (“Not at all”) to 3 (“Nearly every day”) and one additional item measuring how the symptoms affect functioning. The Patient Health Questionnaire-9 (PHQ-9; (Kroenke, Spitzer & Williams 2001) measures depression severity. The measure consists of nine items scored from 0 (“Not at all”) to 3 (“Nearly every day”). The Work and Social Adjustment Scale (WSAS; (Mundt et al. 2002) measures impairment in functioning. The measure consists of five items scored from 0 (not at all impaired) to 8 (very severely impaired). CORE-OM (Evans et al. 2002) is a 34-item self-report, measuring well-being, symptoms, elements of risk, and function on a five-point scale ranging from “not at all” to “most, or all the time”. CORE-10 (Barkham et al. 2013) is a ten item self-report measuring symptoms, well-being, functioning and risk on a five-point scale ranging from “not at all” to “most, or all the time”. The Negative Effects Questionnaire (NEQ) (Rozental et al. 2016, Rozental et al. 2019) is a 20-item questionnaire evaluating adverse or unwanted events during treatment. Participants report whether a specific event occurred during treatment (“Yes”/”No”) and then indicate how negatively they were affected by it on a scale ranging from 0-4. An adapted version of the Credibility Rating Scale (Borkovec & Nau 1972) will be used to assess treatment credibility. The scale consists of five items where participants rate their credibility/expectancy-for-improvement on a 10-point scale.

**System data on user behaviour.** Data on use and user behaviour will be extracted from the system and combined with data from the self-report questionnaires collected. Information about the actual program use will be generated by the e-health platform Youwell. The data includes the extent to which participants complete the treatment, where and when they drop out, and how long they need to complete individual parts. Further we will look into whether there are areas in the treatment that require more time than others, which elements are used

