## **Intervention**

The treatment intervention is a digital transdiagnostic work-focused cognitive behaviour therapy program. The program consists of seven modules (See Table 1 for an overview, and Appendix B for an in-depth review of the modules) consisting of psychoeducational texts, imagery and models, in addition to therapist-tailored tasks for the

participants. The treatment model is based on traditional CBT principles and adjusted to target transdiagnostic maintaining mechanisms in anxiety and depression such as frequent negative emotions and aversive reactions to these that leads to various forms of avoidant coping that serve to reinforce the negative emotional cycle.

*Table 1.*

The modules of the digital program eBehandling – Health and Work

Module 1	Introduction to the program
Module 2	Where can I get help? How can I support myself?
 Module 3	Self-help through constructive and supporting thoughts
Module 4	Helpful actions
Module 5	Working with/through the body
Module 6	Emotions
Module 7	Put it all together and relapse prevention

Treatment will be given by trained eTherapists with specific training in the eBehandling - health and work protocol. They will be given a two-day certified course in work-focused therapy delivered by the National Centre of Competence at Vinderen DPS. Further they will be given a one-day introduction on the use of W-CBT within a digital format by the authors of the program. Further supervision will be facilitated by the research fellow. Adherence and fidelity will be measured through reading eTherapist-participant correspondence and will be rated by the main author of the treatment protocol ([name]) and the main author of the Norwegian translation of W-CBT, [name].

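### Inclusion criterion 4, read as printed (F30 – F40), leaves out every primary anxiety or stress diagnosis from F41 onward and so does not match the anxiety-and-depression population the protocol describes

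*Protocol*

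**What the plan says.** The diagnostic population is fixed in one place, inclusion criterion 4 in the Sample section: "primary diagnosis of F30 – F40 (ICD-10"). No other part of the protocol gives a code range or explains this one. Two exclusions in the same section bear on it: "ongoing psychotic disorder and/or mania" and "ongoing episode of major depression".

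The population the study is meant to serve is described elsewhere:

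- Background and status of knowledge: "Major depression and anxiety are the most prevalent of the mental disorders and are therefore named common mental disorders (CMD").
- Study aims: "patients with common mental health disorders on sick leave or work assessment allowance".
- Intervention: the treatment model is "adjusted to target transdiagnostic maintaining mechanisms in anxiety and depression".

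Hypothesis H2 expects a large reduction in symptoms of depression and of anxiety. The anxiety outcome, the GAD-7, "is a measure of worry and anxiety and consists of seven items". Under Measures, the eTherapist is to report primary and secondary ICD-10 diagnoses, but no expected distribution of diagnoses is given.

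**The concern.** An eligibility range has to describe the population named in the aim. This one ends at the first anxiety category. A site that follows it to the letter must turn away a sick-listed outpatient whose primary diagnosis is generalised anxiety disorder or panic disorder, although that patient fits the population in the background, the aim and the description of the programme.

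Two things are at stake. The first is whom the results apply to. In a single-arm study, pre-post change describes whoever was enrolled, and no control group shares a shift in case mix. The second is consistency. Recruitment runs through outpatient facilities in two regional health authorities, with eligibility assessed patient by patient. Each location also keeps counts of assessments, inclusions and exclusions, from which acceptance is to be judged. If some sites read the range as printed and others as the F30s and the F40s together, diagnostic mix would differ by site and those counts would not measure the same thing.

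**Working it through.** No arithmetic applies, and there is no plan figure to reproduce. The check sets the criterion beside the rest of the protocol. The protocol does not spell out the codes; their meanings are those of the ICD-10 classification that the criterion names.

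**Step 1: what the printed range contains.**

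- F30: manic episode. Inside.
- F31: bipolar disorder. Inside.
- F32 and F33: depressive disorders. Inside.
- F34 to F39: other mood disorders. Inside.
- F40: phobic anxiety, including social anxiety disorder. Inside.
- F41: panic, generalised and mixed anxiety. Outside.
- F42: obsessive-compulsive disorder. Outside.
- F43: stress and adjustment reactions. Outside.

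**Step 2: comparison with the stated target.** The background defines common mental disorders as major depression and anxiety, the aim uses that term, and the intervention is built for both conditions. None of these places restricts anxiety to phobic disorders. F41 therefore falls within the stated target and outside the printed range. F42 and F43 are not named as targets anywhere, so their intended status is unknown. The same holds for F31, which is inside the range but not named in the aim.

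**Step 3: is the range explained as shorthand?** No section shown says that it stands for the blocks F30–F39 and F40–F48. At least two populations are therefore compatible with the text: the literal one, which stops at F40, and the two-block one, which also admits F41, F42, F43 and the rest of the F4x block.

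**Step 4: the effect of the exclusions.** The exclusion of an ongoing major depressive episode narrows the mood part of the range, so the anxiety codes carry more weight in deciding who remains. The exclusion of ongoing mania works under either reading.

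**Step 5: size.** The share of otherwise eligible patients with a primary diagnosis from F41 onward is not given. From the protocol alone it could lie anywhere between 0% and 100%. The power section does not use diagnosis as an input, so the planned N = 390 does not depend on it.

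**The case against.** The strongest reply is that clinicians will take the range to mean the mood block and the anxiety and stress block. The background, aim and intervention make that plausible. eTherapists are trained in the programme's protocol and receive guidance at their workplace and from the project group, and the implementation directive in Appendix C, which is not shown, may settle the matter. What stands is that divergence between sites is a possibility and has not been shown. What does not stand is that the text is therefore adequate: the eligibility criterion itself carries no such explanation, and the looser reading brings in codes the protocol never names.

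A reader might also infer four stronger things, which the document does not support.

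- *That most anxiety patients are shut out.* No diagnosis mix is given, and F40 retains the phobic disorders. These include social anxiety disorder, the condition in the study used as a proxy for the mediation power calculation. Only the loss of primary diagnoses from F41 onward can be stated.
- *That including F30 contradicts the exclusion of mania.* Exclusions narrow an inclusion range. A patient with ongoing mania is excluded under either reading, so the overlap is untidy but does not change who is enrolled.
- *That H2 cannot be answered for anxiety.* H2 concerns symptoms, and the GAD-7 is a symptom score analysed without restriction by diagnosis. Criterion 4 limits only the primary diagnosis, and no exclusion bars a secondary anxiety diagnosis. The literal range limits generalisation; it does not prevent the analysis.
- *That recruitment would be slowed by a calculable factor.* Any figure would rest on a guessed share of patients lost.

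**Conclusion.** The point holds as a mismatch between a stated eligibility rule and the stated target population. Followed as printed, criterion 4 admits patients with a mood or phobic primary diagnosis and rejects every primary anxiety or stress diagnosis from F41 onward. The anxiety conclusions would then generalise only to patients with a mood or phobic primary diagnosis, which is narrower than the aim. If the two-block reading was intended, the text does not say so, and sites could differ.

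The conclusion rests on the ICD-10 meanings of the codes and on the absence of any explanation of the range in the protocol shown. The number of patients affected cannot be estimated from the document, and no sample-size or power figure changes. Eligibility belongs in the protocol, so an unseen analysis plan would not repair it.

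**What to change.** Replace the range in criterion 4 with an explicit list of the ICD-10 codes or blocks the investigators intend. Reconcile that list with the definition of common mental disorders in the background, the population in the study aims, the programme's target in the Intervention section, and the exclusions in the Sample section. State for each of F31, F41, F42 and F43 whether it is in or out. Which diagnoses are eligible is for the investigators to decide; the review asks only that the passages agree. Send the clarification to all sites.

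For patients already enrolled, tabulate primary diagnosis by site from the codes the eTherapists already report. This would show whether the range has been applied differently, and needs no new data collection.

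The cost is a minor amendment of one line and a note to sites. If the clarification changes who is enrolled, the diagnostic mix before and after it has to be described when results are reported.
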